4.5. Supportive Care Guidelines

4.5.1. Supportive measures including blood and platelet transfusions, antimicrobials, and analgesics are permitted.

4.5.2. The administration of anticancer therapies, other investigational cytotoxic agents, or prophylactic use of hematopoietic colony stimulating factors are not permitted.

4.5.3. Erythropoietin or hematopoietic colony stimulating factors for treatment of cytopenias are discouraged. If administered, the subject will not be eligible for a HI response assessment within one week of the receipt of epoetin alfa, filgrastim, or sargramostim, or for one month after receipt of pegfilgrastim or darbopoetin.

4.5.4. Platelet Transfusions: Platelet transfusion data must be captured on the case report form during the screening, treatment and extension periods. A unit of platelets is defined as a single unit of platelet-rich plasma or buffy-coat concentrate or 1 apheresis (single donor) concentrate. The number of units transfused must be recorded.

ASCO guidelines suggest platelet transfusion criteria of:

- Platelet count < 10 x 10⁹/L
- Signs of hemorrhage
- Subject with a high fever and platelet count < 20 x 10⁹/L
- Subject has a hyperleukocytosis
- There has been a rapid fall in platelet count and transfusions will not be readily available in case of emergencies

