6.2. Study Endpoints

6.2.1. Primary Efficacy Endpoint: The overall response rate (CR + PR + HI) based on the IWG-2006 criteria. Responses must last at least 4 weeks.

Complete Remission:

- Bone marrow: $\leq 5\%$ myeloblasts with normal maturation of all cell lines
- Persistent dysplasia will be noted
- Peripheral blood
 - o Hemoglobin $\geq 11\text{g/dL}$
 - o Platelets $\geq 100 \times 10^9/\text{L}$
 - o Neutrophils $\geq 1.0 \times 10^9/\text{L}$
 - o Blasts 0%

Partial Remission:

- All CR criteria if abnormal before treatment except:
 - o Bone marrow blasts decreased by $\geq 50\%$ over pretreatment but still $> 5\%$

Stable Disease:

- Failure to achieve at least PR, but no evidence of progression for >8 weeks

Failure:

- Death during treatment or disease progression characterized by worsening of cytopenias or significant increase in percentage of bone marrow blasts

Hematologic Improvement (HI) Response Criteria*: responses must last at least 8 weeks

- **Erythroid response** (if pretreatment hemoglobin $< 11\text{g/dL}$)
 - o Hemoglobin increase by $\geq 1.5\text{g/dL}$
 - o Relevant reduction of units of RBC transfusions by an absolute number of at least 4 RBC transfusions/8 wk compared with the pretreatment transfusion number in the previous 8 wks. Only RBC transfusions given

for a Hgb of ≤ 9.0 g/dL pretreatment will count in the RBC transfusion response evaluation

- **Platelet response** (if pretreatment platelets $< 100 \times 10^9/L$)
 - o Absolute increase of $\geq 30 \times 10^9/L$ for patients starting with $> 20 \times 10^9/L$ platelets
 - o Increase from $< 20 \times 10^9/L$ to $> 20 \times 10^9/L$ and by at least 100%
- **Neutrophil response** (if pretreatment $< 1.0 \times 10^9/L$)
 - o At least 100% increase and an absolute increase of $> 0.5 \times 10^9/L$

*Pretreatment counts averages of at least 2 measurements (not influenced by transfusions) for at least one week

Progression or relapse after HI‡:

- At least 1 of the following:
 - o At least 50% decrement from maximum response levels in granulocytes or platelets
 - o Reduction in hemoglobin by ≥ 1.5 g/dL
 - o Transfusion dependence
- ‡In the absence of another explanation, such as acute infection, repeated courses of chemotherapy (modification), gastrointestinal bleeding, hemolysis, and so forth. It is recommended that the 2 kinds of erythroid and platelet responses be reported overall as well as by the individual response pattern.

Relapse after CR or PR:

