8.4.2. Analysis of Key Study Endpoints

The primary endpoint is overall response rate (ORR). The ORR in each arm will be evaluated along with the exact 95% confidence interval. Given the limited sample size, no formal comparison will be made between these two arms in terms of ORR.

Secondary endpoints include platelet response, durable platelet response, transformation to AML, incidence of bone marrow fibrosis, and time-to-event outcomes such as progression-free survival (PFS) and overall survival (OS). The probabilities of PFS and OS will be estimated using the method of Kaplan and Meier. The incidence rates of other binary secondary endpoints will be estimated, along with the exact 95% confidence intervals. Subjects that discontinue the study prior to having achieved a clinical response will be considered to have not had an event.

Patients receiving growth factors other than eltrombopag (erythropoietin, GM-CSF or G-CSF) will not be considered in the HI analysis for the time periods specified in Section 4.5.3 Supportive Care Guidelines. Hemoglobin levels and platelet counts collected from patients that have received a transfusion within the last 3 days will not be considered in the analysis.

Survival or times to failure and time to progression functions will be estimated using the Kaplan-Meier method. The two-sided log-rank test will be used to assess the differences of time to events between groups.

The total number of dose administrations, the average dose (mg), and the cumulative dose administered will be summarized by eltrombopag treatment group.

Blood chemistry and complete blood counts will be summarized by treatment group at each time point.

Additional exploratory analyses of the key study endpoints will be performed as deemed appropriate.

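### The growth-factor exclusion covers only HI, so a supported hemoglobin or neutrophil count can complete a CR or PR in the primary ORR; the gap is narrow but cheap to close

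*Combined protocol and SAP*

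**What the plan says.** Section 6.2.1 defines the primary endpoint as "The overall response rate (CR + PR + HI) based on the IWG-2006 criteria. Responses must last at least 4 weeks". HI carries its own, longer requirement of 8 weeks. CR requires hemoglobin of at least 11 g/dL, platelets of at least 100 × 10⁹/L, neutrophils of at least 1.0 × 10⁹/L, no blood blasts and at most 5% marrow myeloblasts. PR takes over those requirements ("All CR criteria if abnormal before treatment except") and changes only the marrow item, to a blast reduction of at least half with more than 5% remaining. Neither definition mentions growth factors. The footnote on pretreatment counts for HI guards against transfusion effects only.

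Section 4.5.2 states that "prophylactic use of hematopoietic colony stimulating factors are not permitted". Section 4.5.3 is softer on therapeutic use: "Erythropoietin or hematopoietic colony stimulating factors for treatment of cytopenias are discouraged". Its consequence is limited to one component of the endpoint: "If administered, the subject will not be eligible for a HI response assessment within one week of the receipt of epoetin alfa, filgrastim, or sargramostim", with a window of one month for pegfilgrastim and darbepoetin. Section 8.4.2 repeats that scope: such patients "will not be considered in the HI analysis for the time periods specified in Section 4.5.3 Supportive Care Guidelines". No other section extends the rule to CR or PR.

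**The concern.** The windows in section 4.5.3 accept that these agents make counts unreliable as evidence of response for a week or a month. The same neutrophil count is then rejected for a neutrophil HI but accepted for a CR or PR, which feed the same primary endpoint and face the shorter duration test (4 weeks against 8). A supportive treatment that is allowed could supply the last missing criterion of a response credited to study treatment. The success cut-offs are 3 of 23 (Arm A) and 4 of 23 (Arm B), and each first stage stops on zero responses, so a single such patient can matter.

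**Working it through.** **1. The rules side by side**

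| Component of ORR | Uses hemoglobin or neutrophils | Duration | Growth-factor exclusion |
|---|---|---|---|
| CR | Yes | 4 weeks | None stated |
| PR | Yes, if abnormal before treatment | 4 weeks | None stated |
| HI | Yes (erythroid, neutrophil) | 8 weeks | 4.5.3 and 8.4.2 |

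**2. When the ORR changes.** Every patient enters with platelets below 100 × 10⁹/L (section 3.1, criterion 4), so a CR or PR always needs a platelet rise to at least 100, as well as the marrow criterion. Compare that with platelet HI in section 6.2.1:

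- Baseline above 20 and up to 70: reaching 100 is a gain of at least 100 − 70 = 30, which meets the HI size threshold.
- Baseline below 20: reaching 100 passes 20 and is more than a doubling, which also meets it.
- Baseline of about 71 to 99: reaching 100 can be a gain of less than 30, so platelet HI may fail.

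A supported count therefore adds a responder to the ORR only if the patient has no other qualifying unsupported HI. That can happen with baseline platelets of about 71–99, with a response lasting 4 to under 8 weeks, or where the growth-factor window itself blocks HI assessment. The supported count must also be maintained for 4 weeks.

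A constructed example: marrow blasts fall from 12% to 6%, platelets rise from 80 to 102 and hemoglobin is 11.2 g/dL throughout. Neutrophils rise from 0.6 to 1.4 under repeated or long-acting CSF, and all counts hold for 4 weeks. The blast fall is 6/12 = 50% with more than 5% remaining, so the written PR criteria are met. The platelet gain of 22 is short of 30, erythroid HI does not apply, and HI assessment is barred in the window. The overall response rests on the supported neutrophil count.

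**3. The plan's own operating characteristics (section 8.2.1).** With n₁ first-stage patients, 23 in total, r responses needed and a stop at zero:

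P(success) = Σ (x = 1 to n₁) P(X₁ = x) × P(X₂ ≥ r − x), with X₁ ~ Bin(n₁, p) and X₂ ~ Bin(23 − n₁, p).

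- Arm A (n₁ = 15, r = 3, p = 5%): 0.3658 × 0.0572 + 0.1348 × 0.3366 + 0.0362 = 0.1025.
- Arm B (n₁ = 12, r = 4, p = 5%): 0.3413 × 0.0152 + 0.0988 × 0.1019 + 0.0173 × 0.4312 + 0.0022 = 0.0250.

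| | Arm A stated | Arm A computed | Arm B stated | Arm B computed |
|---|---|---|---|---|
| Type I error | 10.3% | 10.2% | 3% | 2.5% |
| Power (at 18% / 25%) | 80% | 80.2% | 85% | 85.4% |
| Early stop at 5% | 46.3% | 46.3% | 54% | 54.0% |
| Expected N at 5% | 19 | 19.3 | 17 | 17.1 |

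The plan's figures reproduce, apart from rounding. The issue is the response definition, not the design arithmetic.

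**4. Sensitivity.** The documents give no rate of growth-factor use or of CR/PR completed by it. The added points below are assumptions, put into the same formula at p = 5% plus the increment.

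| Added to a true 5% ORR | Extra responders expected in 23 | Arm A success | Arm B success |
|---|---|---|---|
| 0 points | 0 | 10.2% | 2.5% |
| 1 point | 0.23 | 15.3% | 4.5% |
| 2 points | 0.46 | 21.0% | 7.1% |
| 3 points | 0.69 | 27.2% | 10.4% |
| 5 points | 1.15 | 40.0% | 18.7% |

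**5. One patient.** Suppose one first-stage response rests on a supported count and the other 22 patients respond at 5%. The zero-response stop is lifted, and success needs at least 2 of 22 in Arm A or at least 3 of 22 in Arm B. The chances are 30.2% and 9.5%. At the Arm A boundary, 3/23 is 13.0% (exact 95% CI 2.8 to 33.6) and passes; 2/23 is 8.7% (1.1 to 28.0) and fails.

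**The case against.** The strongest reply is that the gap will rarely be used. Three parts of it stand.

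- Growth factors alone cannot make a CR or PR. The patient must also reach platelets of 100 and meet the marrow criterion, so at most a supported count supplies the last missing item in someone with real improvement. Calling that a false response is itself debatable.
- Most such patients reach the platelet HI size threshold anyway.
- One raised count after a short-acting dose does not score a PR. The response must last 4 weeks, while therapeutic use is discouraged and prophylactic CSF is barred.

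Two further points limit confidence without closing the gap. The criteria are said to be based on IWG-2006, and whether that source restricts growth factors for CR or PR cannot be checked from these documents; the protocol's written criteria do not. The next sentence of section 8.4.2 excludes post-transfusion values from the analysis without naming HI. That may signal a deliberately wider scope or may refer back to the HI analysis, so nothing here relies on it.

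A reader might infer that the type I error is really 27% in Arm A or 19% in Arm B. The documents do not support that, because those values need assumed increments of 3 and 5 points. A reader might also infer that Arm B is inflated more because the HMA continues. Section 2.1 describes myelosuppression as common with HMAs, which makes greater CSF use there plausible, but no growth-factor rate is given for either arm.

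**Conclusion.** The gap is real on the text. As written, the plan accepts for CR and PR a hemoglobin or neutrophil value that it rejects for HI, and all three enter the primary ORR. Its reach is narrow: a patient who already meets the platelet and marrow criteria, whose supported count lasts 4 weeks, and who has no qualifying unsupported HI. The size cannot be estimated from the documents. Over the assumed 1 to 5 points, the chance of success at a true 5% ORR is 15.3–40.0% in Arm A (against 10.2%) and 4.5–18.7% in Arm B (against 2.5%). The low end is already an assumption and the high end only shows how sensitive small cut-offs are. Low-to-moderate priority, worth settling because the change is small.

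**What to change.** In sections 4.5.3 and 8.4.2, state the exclusion at the level of values, keeping the existing windows:

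- Within the window, a hemoglobin value after an erythropoietic agent, or a neutrophil value after a CSF, may not be used to meet a CR, PR or HI count criterion or its 4- or 8-week duration, nor as a pretreatment reference count.
- Unaffected lineages and the marrow remain assessable.
- An excluded value counts neither for nor against the duration.
- A patient with no qualifying unsupported count stays in the denominator as a non-responder.

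Simply adding CR and PR to the present wording would be too blunt. Section 4.5.3 makes the subject ineligible for assessment, so a patient on darbepoetin could lose a month in which neutrophils, platelets and marrow are unaffected. The value-level rule also narrows the present HI exclusion, because platelet HI becomes assessable inside the window; the amendment should say so.

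The cost is small. Concomitant medications are already collected throughout (section 4.1.5, Table 5.3). The sample size, the cut-offs and the rules on when growth factors may be given are unchanged. The downside is that the ORR may be slightly lower, and a few genuine responders with growth-factor exposure may be confirmed later or missed.

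### The 3-day transfusion exclusion does not match blood product to laboratory value, so as worded a red-cell transfusion discards a valid platelet count, and a platelet transfusion a valid hemoglobin

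*Combined protocol and SAP*

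**What the plan says.** Section 8.4.2 of the combined protocol and SAP states the rule: "Hemoglobin levels and platelet counts collected from patients that have received a transfusion within the last 3 days will not be considered" in the analysis. It does not say which product excludes which value.

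The values concerned are used as follows:

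- Section 6.2.1 defines the primary endpoint as "The overall response rate (CR + PR + HI) based on the IWG-2006 criteria". For HI, "responses must last at least 8 weeks". Platelet and hemoglobin thresholds also appear in the complete remission, relapse and progression criteria.
- Section 8.4.2 adds the platelet endpoints: "Secondary endpoints include platelet response, durable platelet response".
- For baseline, the HI footnote in Section 6.2.1 asks for "Pretreatment counts averages of at least 2 measurements (not influenced by transfusions) for at least one week". This is a test of influence, not of elapsed time, and it does not name a product either.
- Section 4.5.1 allows both kinds of transfusion: "Supportive measures including blood and platelet transfusions, antimicrobials, and analgesics are permitted".

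**The concern.** A transfusion exclusion is there to keep a transfused product from being mistaken for recovery of the patient's own counts. That purpose is served by dropping platelet counts after platelets and hemoglobin after red cells. Red cells do not raise the platelet count, and platelets do not raise hemoglobin. The cross-exclusions therefore remove no artefact and only delete usable measurements.

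Every patient enters with platelets below 100 × 10⁹/L (Section 3.1), and platelet improvement is the response most expected from the drug's mechanism. A patient who still needs red cells would lose platelet counts inside the 8-week period over which that improvement has to be shown. The arm-level decisions turn on few patients: no responders among 15 (Arm A) or 12 (Arm B) stops an arm, and 3 or 4 of 23 is success (Section 8.2.1). A programmer who follows the sentence literally would be deleting primary-endpoint data.

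The baseline and on-study rules also fit together poorly. A platelet count taken two days after red cells alone was not influenced by the transfusion, so it can qualify at baseline. The same count on treatment would be discarded.

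**Working it through.** **Text.** Three places bear on transfused counts.

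| Place | Test applied | Product named? |
|---|---|---|
| Section 8.4.2, analysis rule | Any transfusion in the prior 3 days | No |
| Section 6.2.1, HI footnote (baseline) | Count influenced by transfusion | No |
| Section 4.7.1.2 (dose adjustment) | Untransfused platelet count | Not explicitly |

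The last two lean towards product matching, but neither governs how on-study counts are scored for response. No other section does so.

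**Design figures.** The rule carries no number of its own. An exact two-stage binomial calculation of the designs that it feeds gives:

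- Arm A (stop at 0/15, success at 3 or more of 23, 5% versus 18%): power 80.2%, early termination 46.3%, expected size 19.3. Stated: 80%, 46.3%, 19.
- Arm B (stop at 0/12, success at 4 or more of 23, 5% versus 25%): power 85.4%, early termination 54.0%, expected size 17.1. Stated: 85%, 54%, 17.

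Rewording the transfusion rule changes none of these.

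**Share of days blocked for platelet counts by red cells.**

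Inputs from the documents:

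- The exclusion window is 3 days (Section 8.4.2).
- The HI duration is 8 weeks, or 56 days (Section 6.2.1).
- Blood counts are weekly until stable (Table 5.3, note 1).
- The only red-cell frequency given is in the erythroid criterion: "Relevant reduction of units of RBC transfusions by an absolute number of at least 4 RBC transfusions/8 wk". It is a response threshold expressed in units, not an observed burden.

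Assumptions: episodes are evenly spaced, draw days are unrelated to transfusion days, and the 4 are either 4 separate episodes or 2 episodes of two units each.

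Formula: blocked share = 3 × episodes ÷ 56.

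- 2 episodes: 6/56 = 10.7%. Of 8 weekly counts, 8 × 0.107 = 0.9 is lost.
- 4 episodes: 12/56 = 21.4%. Of 8 weekly counts, 8 × 0.214 = 1.7 are lost.

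If the day of transfusion is counted as a fourth day, the shares become 8/56 = 14% and 16/56 = 29%. If counts have stabilised and only the Day 1 cycle visits remain, 8 weeks holds about 3 counts (days 0, 28 and 56), and the expected loss is 3 × 0.107 = 0.3 to 3 × 0.214 = 0.6 of a count.

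**What these shares measure.** On the draw-timing assumption they are upper bounds on the excess loss at those frequencies. A platelet count that also follows a platelet transfusion would be dropped under a product-matched rule too, and the documents do not allow that overlap to be subtracted. If each draw precedes the transfusion and the previous one is more than 3 days back, the loss is near zero.

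**The reverse case.** The same formula applies to hemoglobin values lost after platelet transfusions, but the documents give no platelet-transfusion frequency to put in.

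**The case against.** The strongest reply is that the sentence can be read respectively: hemoglobin after red cells, platelets after platelets. The wording in Sections 6.2.1 and 4.7.1.2 fits that intent. This reading is possible, and the authors may well have meant it. It does not remove the point, because the sentence does not say so and the analysis would be programmed from the sentence.

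The reply is stronger on size, and most of it stands:

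- **Frequency.** A reader might infer that weekly or twice-weekly red cells would block 3/7 (43%) or 6/7 (86%) of days. The documents describe no such burden. Even at twice weekly, 3.5 days apart, a count drawn just before each transfusion falls outside the previous 3-day window and is kept.
- **Scorability.** A reader might infer that red-cell-dependent patients become unscorable for platelet response. The rule drops values, not patients. Section 6.2.1 sets no minimum number of counts for the 8-week duration, and Section 6.1 allows assessment up to 6 cycles (6 × 28 = 168 days), so there may be time to confirm a response.
- **Bias and power.** A reader might infer that the rule lowers ORR and costs power against the thresholds of 3/23 and 4/23. Any such figure needs an assumed share of missed responders, and the documents supply none. Nor is the direction fixed: a dropped count may hide a rise, or it may hide a dip that would have ended a response.

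**Conclusion.** The point holds as a defect in a stated analysis rule. Taken literally, Section 8.4.2 discards valid platelet counts after red-cell-only transfusions and valid hemoglobin values after platelet-only transfusions, and no other section corrects this. The values feed the primary endpoint and both platelet secondary endpoints.

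The size is modest and partly unknown. The loss ranges from near zero, with draws before transfusion, to about 11% to 21% of days at 2 to 4 red-cell episodes per 8 weeks. The upper figures rest on a 3-day window, even spacing and draws unrelated to transfusion. Neither the size nor the direction of any effect on ORR can be derived from the documents, which also do not say how excluded counts are treated when the 8-week duration is judged. The correction is worth making before responses are scored, but it gives no reason to revisit the sample size or the decision thresholds.

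**What to change.** Replace the sentence in Section 8.4.2 with:

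> Platelet counts within 3 days after a platelet transfusion, and hemoglobin values within 3 days after a red-cell transfusion, will not be used to score response; a transfusion of one product does not exclude the other value.

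This leaves the length of the window and the growth-factor rule as they are. If product matching was always intended, it only makes that explicit.

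The cost is small. The date and product of every transfusion, red cells included, must be recorded and used in programming. Section 4.5.4 explicitly requires only platelet transfusion data and units. Red-cell data are already implied by the erythroid criterion in Section 6.2.1 and by the transfusion assessment in Table 5.3, but the case report form should be checked for red-cell dates.

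### On-treatment hemoglobin and platelet counts taken from day 4 after a transfusion can support hematologic improvement, and so the primary ORR, because the response window has no transfusion-free rule of its own.

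*Combined protocol and SAP*

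**What the plan says.** The primary efficacy endpoint in section 6.2.1 is "The overall response rate (CR + PR + HI) based on the IWG-2006 criteria", so every HI counts in full toward the ORR.

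- **Before treatment.** The footnote to the HI criteria in 6.2.1 reads "Pretreatment counts averages of at least 2 measurements (not influenced by transfusions) for at least one week".
- **In the analysis.** Section 8.4.2 says that hemoglobin and platelet counts from patients who "have received a transfusion within the last 3 days will not be considered in the analysis". The sentence is not restricted to either period.
- **Erythroid HI.** One route is "Hemoglobin increase by" at least 1.5 g/dL. The other is "Relevant reduction of units of RBC transfusions by an absolute number of at least 4 RBC transfusions/8 wk compared with the pretreatment transfusion number", which accepts continuing transfusion.
- **Platelet HI.** The criterion is a rise of at least 30 x 10^9/L, or at least a doubling from below 20 to above 20 x 10^9/L. Neither the hemoglobin nor the platelet route requires freedom from transfusion.
- **Duration and loss.** Under HI, "responses must last at least 8 weeks"; under the primary endpoint as a whole, "Responses must last at least 4 weeks". "Transfusion dependence" is listed as progression or relapse after HI, without a definition.
- **Conduct.** Section 4.5.1 permits blood and platelet transfusions. Table 5.3 asks for weekly counts until they are stable, and otherwise on Day 1 of each cycle from cycle 2, with extra counts after a change in eltrombopag dose.

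**The concern.** HI by hemoglobin or platelets is a change from baseline. The plan treats transfusion as a contaminant when it fixes the baseline. For the follow-up value, its only protection is the 3-day exclusion. A patient transfused repeatedly during the response window can supply counts four or more days after each transfusion, and those counts are usable. If they sit high enough above baseline, the patient is scored as a responder although the rise came from donor cells.

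The protocol is aware of the distinction: section 4.7.1.2 specifies an untransfused platelet count for the dose-adjustment trigger, but 6.2.1 does not carry that qualifier into the response criteria.

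The design has little room for false responses. Under section 8.2.1 an arm succeeds with 3 of 23 (Arm A) or 4 of 23 (Arm B) against a 5% null, and a single first-stage response opens the second stage. The arms are not randomized (5.2) and are not formally compared on ORR (8.4.2), so no control group would reveal the inflation.

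**Working it through.** **Step 1. Reproduce the design.** Inputs are from section 8.2.1. Arm A: n1 = 15, N = 23, success at 3 or more, null 5%, target 18%. Arm B: n1 = 12, N = 23, success at 4 or more, null 5%, target 25%. Each arm stops if the first stage has no response. With r the success cut-off,

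P(success | p) = sum over x >= 1 of Bin(x; n1, p) x P[Bin(N - n1, p) >= r - x].

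At p = 0.05:

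- Arm A: x = 1 gives 0.3658 x 0.0572 = 0.0209; x = 2 gives 0.1348 x 0.3366 = 0.0454; x >= 3 gives 0.0362. The sum is 0.1025.
- Arm B: x = 1 gives 0.3413 x 0.0152 = 0.0052; x = 2 gives 0.0988 x 0.1019 = 0.0101; x = 3 gives 0.0173 x 0.4312 = 0.0075; x >= 4 gives 0.0022. The sum is 0.0250.

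| | Arm A plan | Arm A exact | Arm B plan | Arm B exact |
|---|---|---|---|---|
| Type I error | 10.3% | 10.2% | 3% | 2.5% |
| Power | 80% | 80.2% | 85% | 85.4% |
| Early stop at 5% | 46.3% | 46.3% | 54% | 54.0% |
| Expected N at 5% | 19 | 19.3 | 17 | 17.1 |

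The design reproduces. The small differences in type I error do not bear on this point.

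**Step 2. Illustrate false responses.** No document gives a rate of transfusion-driven HI. Assume that it adds 1, 3 or 5 points to a true ORR of 5%, and evaluate the same formula at p = 0.06, 0.08 and 0.10.

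| Scored ORR | Arm A P(success) | Arm B P(success) |
|---|---|---|
| 5% (no false responses) | 10.2% | 2.5% |
| 6% | 15.3% | 4.5% |
| 8% | 27.2% | 10.4% |
| 10% | 40.0% | 18.7% |

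If the error applies only to true non-responders, p = 0.05 + 0.95e. Then e = 1% gives 15.0% and 4.3%, and e = 5% gives 38.4% and 17.6%, which is nearly the same. For scale, one patient in 23 is 1/23 = 4.3 points, so the assumed range is 23 x 0.01 = 0.23 to 23 x 0.05 = 1.15 expected false responders in a full arm.

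**Step 3. Test the existing safeguards.**

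- *Eight-week duration.* One transfusion would not easily meet it. Repeated transfusion, or few counts, could. Once counts are stable and the dose unchanged, 8 weeks is 56/28 = 2 cycle intervals, so the window can rest on about three Day 1 counts. The general 4-week statement in 6.2.1 also leaves the duration bar unclear.
- *Transfusion dependence.* It is undefined, it appears as loss of HI or as disease progression rather than as a condition for scoring HI, and it stands beside an erythroid route that accepts ongoing transfusion.

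**The case against.** The strongest reply has four parts.

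1. *The two ends may share one rule.* A reader might infer that baseline must be transfusion-free for a week and follow-up for only 3 days. The text does not settle this. The week may describe the span of the averaged counts, and the 3-day sentence, which is not limited to on-treatment values, may be what defines freedom from transfusion influence at baseline too. This stands. Even then, counts from day 4 are admitted throughout the response window.

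2. *The bias need not favor response.* A reader might infer that it always does. If the 3-day rule also governs baseline, transfusion can raise the baseline and hide a response. Excluded counts can also leave a true response unconfirmed. This stands.

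3. *The mechanism has limits.* A patient transfused at the same trigger before and after Day 1 returns to similar troughs, and those troughs are usable counts that would break an 8-week rise. False erythroid HI therefore needs more liberal transfusion on treatment or sparse counts. For platelets the mechanism is weak: section 2.1 calls the effect of transfusion short-lived, and section 4.5.4 cites a guideline threshold below 10 x 10^9/L, so holding a 30 x 10^9/L gain for 8 weeks on transfusion is hard to picture. This stands and is why the point rests mainly on HI-E.

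4. *Transfusion dependence would catch the worst cases.* Perhaps, once defined. As written it leaves the decision to the assessor.

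**Conclusion.** The gap is real. The plan states a definite rule that admits hemoglobin and platelet counts from day 4 after a transfusion, and it places no transfusion condition on the counts that establish HI. Such counts can therefore enter the primary ORR, most plausibly through the hemoglobin route of HI-E.

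Its size cannot be derived from the documents. A reader might infer from the illustrative range (15.3-40.0% in Arm A, 4.5-18.7% in Arm B) that the type I error is inflated by that much. The documents do not support that inference: the 1 to 5 points are assumed, and the same figures would follow from any misclassification of that size. They show only that about one false responder per arm would matter against cut-offs of 3 and 4 in 23. With no such misclassification the design keeps its 10.2% and 2.5%.

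**What to change.** In section 8.4.2, state one transfusion-free window for all hemoglobin and platelet values used to score HI, at baseline and on treatment. Use the one week named in 6.2.1, and say that it replaces the 3-day rule for HI scoring. This also resolves the ambiguity in the baseline footnote.

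Add a sensitivity analysis: the ORR in each arm after excluding HI-E responses that rest on a hemoglobin rise in patients given RBC transfusions during the 8-week window. A harder rule, confining any RBC-transfused patient to the transfusion-reduction route, is not advised. A patient with fewer than 4 transfusions in the 8 weeks before treatment cannot show a reduction of 4, so one incidental transfusion would put HI-E out of reach in that window.

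While the text is open, define transfusion dependence for loss of HI and reconcile the 4-week and 8-week durations.

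The cost is analysis wording, with no change to treatment. Section 4.5.4 requires platelet transfusions on the case report form but gives no matching instruction for RBC units, so confirm that RBC transfusion dates are captured. The downside is that some counts in heavily transfused patients become unusable, and a few true responses may go unconfirmed.
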